Asthma and post-traumatic stress disorder (PTSD) are the most common conditions in World Trade Center (WTC) rescue and recovery workers. A large number of WTC workers continue to report poor asthma control and impaired quality of life. Thus, asthma is a major cause of morbidity in this population. Several studies show a strong relationship between PTSD and increased asthma morbidity. PTSD is associated with systemic inflammation (increased levels of interleukin [IL]-1 α , IL-2, IL-6, and tumor necrosis factor-alpha [TNF- α]). Some of these pro-inflammatory cytokines have been linked to more severe asthma phenotypes, potentially explaining the relationship between PTSD and worse asthma outcomes. However, biological pathways are likely only part of the drivers of asthma morbidity. Several observations suggest that PTSD has a stronger association with subjective (asthma symptoms, use of rescue medication, and quality of life) than objective (pulmonary function) markers of asthma morbidity, suggesting over-perception of symptoms. Additionally, theory and empirical evidence suggest that inaccurate perception of asthma symptoms and maladaptive illness and medication beliefs in patients with PTSD may lead to lower adherence to asthma self-management behaviors (SMB), a key determinant of asthma outcomes. With adherence to controller medications being low among asthma patients in general, behavioral mechanisms may also contribute to the association between PTSD and increased asthma morbidity in WTC workers. Our goal is to examine the interaction of biology and behavior in WTC workers with asthma and PTSD and use this information to design and pilot test an intervention to improve their care.

1) Objectives:

Research Question:

Our goal is to examine the interaction of biology and behavior in WTC workers with

 Mount Sinai	Protocol Title:	Assessing Inflammatory and Behavioral Pathways Linking PTSD to Increased Asthma Morbidity in WTC Workers
	Principal Investigator Name/Contact Info:	[name], DrPH [contact]; [contact]
	Primary Contact Name/Contact Info	[name], MS [contact]; [contact]
	Date Revised:	07/25/16
	Study Number:	IF# 1896970; GCO# 16-0945

asthma and PTSD and use this information to design and pilot test an intervention to improve their care. The Specific Aims are to:

1. Assess the relationship of PTSD with systemic and airway inflammatory patterns in WTC workers with asthma and evaluate the association with asthma control

H1a: PTSD will be associated with increased systemic levels of IL-1b, TNF- α and IL-6. H1b: WTC workers with asthma and PTSD will have an increased expression of sputum neutrophilia and IL-6 levels. H1c: Increased sputum neutrophilia and higher IL-6 levels will be associated with poorer disease control among WTC workers with asthma.

2. Examine the longitudinal association between PTSD and symptom perception in WTC workers with asthma

H2a: WTC rescue and recovery workers with PTSD will be more likely to over-perceive asthma symptoms in naturalistic settings compared to participants without PTSD. H2b: Associations between subjective (Asthma Control Questionnaire, use of rescue medications, and Asthma Quality of Life Questionnaire scores) and objective (forced expiratory volume in 1 second [FEV₁]) measures of asthma control will be weaker among WTC workers with PTSD than those without PTSD.

3. Assess the relationship between PTSD and adherence to asthma SMB (medication adherence, trigger avoidance, and inhaler technique) in WTC workers and identify the pathways linking them

H3a: PTSD is associated with lower adherence to SMB among WTC workers with asthma. H3b: Asthma (identity, timeline, and cause), medication beliefs (necessity and concerns about controller medications), and over-perception of symptoms will mediate, in part, the influence of PTSD on SMB.

4. Develop and pilot test an integrated intervention for asthma and PTSD by adapting the Relaxation Response Resiliency Program (3RP), a mind-body program, with counseling to promote asthma SMB, and education to correct over-perception of asthma symptoms

H4: The intervention will be acceptable to WTC workers, change beliefs about asthma, correct symptom over-perception, improve asthma medication adherence and quality of life and reduce symptoms of PTSD. We are currently seeking approval for the observational portion of the study only. We will request IRB approval for the interventional (pilot) phase at a later date, in advance of commencing the pilot.

2) Background

SIGNIFICANCE: Importance of the Problem: Multiple studies have shown a high prevalence of asthma in WTC rescue and recovery workers, local residents, and passersby.^{3-6,28-31} Using data from the National Health Interview Survey (NHIS), we found that WTC workers have twice the risk of asthma compared to the general United States (US) population.^{31,32} Data from the WTCHP shows a 28% cumulative incidence of asthma 9 years after September 11, 2001 among WTC workers.¹ These studies show that asthma is the most prevalent respiratory condition among WTC rescue and

 Mount Sinai	Protocol Title:	Assessing Inflammatory and Behavioral Pathways Linking PTSD to Increased Asthma Morbidity in WTC Workers
	Principal Investigator Name/Contact Info:	[name], DrPH [contact]; [contact]
	Primary Contact Name/Contact Info	[name], MS [contact]; [contact]
	Date Revised:	07/25/16
	Study Number:	IF# 1896970; GCO# 16-0945

recovery workers.

WTC workers with asthma include individuals with prior history of the disease and new cases of irritant-induced asthma.⁴ Many workers with preexistent asthma developed worsening symptoms after WTC-related exposures (WTC-exacerbated asthma). Other workers developed new asthma symptoms without latency during or after WTC exposure and were diagnosed with irritant-induced asthma.³³ Multiple cases of new onset asthma among WTC workers have been reported in the years following exposure to the WTC site; characterization of these cases has been more difficult. Despite this potential heterogeneity, these conditions are frequently grouped in clinical practice as WTC-related asthma and managed similarly.

Studies found substantial burden of asthma morbidity in WTC workers and exposed community members, with reports of poorly-controlled in 34% and very poorly-controlled symptoms in 35% of exposed individuals.⁵ Increased risk of emergency department (ED) visits and hospitalizations as well as poor quality of life in WTC workers with asthma have been reported, showing a major impact on health.⁵

Scientific Premise of Project: PTSD is Associated with Increased Asthma

Morbidity in WTC Workers: Prevalence of psychological symptoms in WTC-exposed populations is high,^{1,3,34-37} with PTSD reported as the most common (~30%) mental health condition.^{1,2} Studies have also found high rates (25-35%) of PTSD comorbidity in WTC workers with asthma.^{3,38,39} Mental health conditions and PTSD in particular, have been associated with increased asthma morbidity.^{5,6} We found that WTC workers with PTSD had worse asthma control, increased healthcare use, and poorer quality of life (see preliminary data). Similarly, a study of WTC workers indicated that severity of PTSD symptoms predicted new onset and worsening of asthma.⁴⁰ Data from studies in the general population have also shown that PTSD is associated with higher asthma morbidity.^{16,19,41-43} In summary, studies have documented a high level of overlap between asthma and PTSD in WTC workers and other exposed populations and have documented that PTSD is a major contributor to increased asthma morbidity. However, the underlying mechanisms explaining this relationship remain unknown.

Potential Biological Pathways Linking PTSD and Asthma Morbidity: The impact of PTSD extends to multiple organ systems as a consequence of changes in the hypothalamic-pituitary axis, the autonomic nervous system, and the immune system.⁴⁴⁻⁵² These PTSD-associated systemic alterations may impact asthma morbidity. PTSD is associated with a basal low-grade systemic inflammation, in particular, increased plasma levels of pro-inflammatory cytokines such as interleukin (IL)-1 α , IL-2, IL-6, tumor necrosis factor-alpha (TNF- α and decreased IL-4, IL-5 ("Th2-cytokines").⁷⁻¹⁰ Airway inflammation, a central feature of asthma, may be modulated by enhanced systemic inflammation as that observed in PTSD.^{8,12-15} Major asthma endotypes, which describe asthma subtypes based on inflammatory mechanisms, include allergic, intrinsic (non-atopic), and noneosinophilic asthma.^{53,54} Allergic asthma is characterized by airway eosinophilia driven by T_H2-dominant inflammation. Noneosinophilic asthma is characterized by airway neutrophilia has been associated with refractory disease,

 Mount Sinai	Protocol Title:	Assessing Inflammatory and Behavioral Pathways Linking PTSD to Increased Asthma Morbidity in WTC Workers
	Principal Investigator Name/Contact Info:	[name], DrPH [contact]; [contact]
	Primary Contact Name/Contact Info	[name], MS [contact]; [contact]
	Date Revised:	07/25/16
	Study Number:	IF# 1896970; GCO# 16-0945

severe exacerbations, and increased risk of intubation.⁵⁵⁻⁵⁸ Key cytokines driving neutrophilic asthma include IL-1 β , IL-6 and IL-17, which are elevated in patients with PTSD.⁵¹ IL-6 directs and stabilized T-cells towards a Th17 subset,⁵⁹⁻⁶² which can then recruit and activate of neutrophils.⁶³⁻⁶⁶ Therefore, systemic inflammatory changes associated with PTSD, may worsen asthma outcomes by driving a neutrophilic asthma phenotype. Identification of the biological pathways underlying worse asthma in patients with comorbid PTSD has important implications for disease management including indications for inhaled corticosteroids (ICS) and new biological drugs and may offer new alternative targets for therapy.^{67,68}

Symptom Perception in Asthma Patients with Comorbid PTSD: Effective asthma SMB requires the patient to recognize and respond (use of rescue medication, contact physician, etc.) to their symptoms.^{69,70} Self-monitoring of symptoms is also key for assessing response to treatment and thus, developing effective self-regulatory mechanisms (i.e., ICS linked to improved symptoms; see theoretical framework). Unfortunately, the symptoms that asthma patients experience do not always align with objective measures of their airway obstruction.⁷¹⁻⁸¹ Experiments have identified 3 asthma symptom perception phenotypes that have important clinical implications: symptom under-perceivers, normal perceivers, and over-perceivers.^{78,82-84} Prior studies have shown a strong relationship between misperception of symptoms and increased asthma morbidity.^{77,85-88}

While PTSD is associated with increased objective and subjective asthma morbidity markers, the associations with subjective measures are stronger.^{16,18} We found that PTSD had strong associations with disease control measures and quality of life in WTC workers with asthma.¹⁷ However, the association with FEV₁ was weaker (see preliminary data). Other studies had similar findings.¹⁶⁻²⁰ These data strongly suggest that over-perception of symptoms may be prevalent among WTC workers with PTSD and may contribute to increased asthma morbidity and complicate SMB.

Our hypotheses for over-perception of symptoms among WTC workers with PTSD is based on Janssens's cognitive-affective model of symptom perception.⁸⁹ A central factor in this model is negative affect common among patients with PTSD.⁹⁰⁻⁹³ Janssens's model⁸⁹ proposes that negative affect will be linked with over-perception of symptoms via an associative learning mechanism. Because asthma exacerbations cause a negative affective state,⁹⁴ an association between such a state and asthma symptoms develops in patients with PTSD. As a consequence, subsequent negative emotional states due to PTSD may results in the report of severe asthma symptoms in the presence of mild or no airway obstruction. The effect of negative affect is most pronounced on the affective component (i.e., unpleasantness dimension) of dyspnea. Thus, PTSD patients may perceive more asthma symptoms due to perceptions of unpleasant sensations of dyspnea.

PTSD is also characterized by a disruption in the ability to regulate emotions,^{91,96-98} which can lead to exaggerated emotional reactions to asthma-symptoms, in turn leading to symptom magnification. One relevant cognitive vulnerability factor common to PTSD and asthma is anxiety sensitivity, the tendency to catastrophically misinterpret the bodily

	Protocol Title:	Assessing Inflammatory and Behavioral Pathways Linking PTSD to Increased Asthma Morbidity in WTC Workers
	Principal Investigator Name/Contact Info:	[name], DrPH [contact]; [contact]
	Primary Contact Name/Contact Info	[name], MS [contact]; [contact]
	Date Revised:	07/25/16
	Study Number:	IF# 1896970; GCO# 16-0945

sensations associated with anxious arousal (e.g., shortness of breath or chest pounding) as threatening.^{99,100} Anxiety sensitivity is more common among patients with asthma, strongly implicated in the experience of dyspnea, and associated with poor asthma control,¹⁰¹⁻¹⁰⁵ and greater behavioral avoidance.¹⁰⁶ Recent work by [name] (Consultant) indicates that anxiety sensitivity, physical concerns in particular, plays a significant role in understanding the PTSD-asthma symptom link in WTC workers (see preliminary data).

Assessing Asthma Symptom Perception: Symptom perception is typically measured in laboratories by self-reported respiratory symptoms while inducing airway constriction with histamine or methacholine.^{78,82,107} However, this approach produces biased data because it generates anxiety and primes patients for certain reactions.^{82,84,107,108} In contrast, measurements in naturalistic settings (e.g., their home), as we propose to do, is a validated method^{87,109} that reduces the emotional threat of the test environment and omits pharmacological techniques and devices that may generate anxiety.⁷⁷

PTSD May Negatively Impact Asthma SMB: Asthma self-management encompasses several complex behaviors such as adherence to controller medications, adequate inhaler technique, use of action plans, allergen avoidance, and avoiding tobacco exposure that are critical for adequate disease control. Adherence to controller medications in particular, is a factor that heavily influences the outcomes of asthmatics.¹¹⁰⁻¹¹² Studies conducted in the general population and our preliminary data from WTC workers shown that only ~50% of patients with asthma adhere to controller therapy or other SMB.^{25-27,113-117}

Mental health conditions are associated with low adherence to chronic disease SMB.¹¹⁸⁻¹²⁰ PTSD, in particular, has been strongly associated with low treatment adherence in multiple chronic diseases.^{21,23,24,121} With smoking being an important part of asthma self-management, it is of special concern that higher rates of smoking have been reported among WTC workers with PTSD.^{122,123} Thus, low adherence to SMB may mediate, in part, the association between PTSD and increased asthma morbidity. However, there is limited data regarding the relationship between PTSD and asthma SMB in the general population or among WTC workers, in particular.

Theoretical Framework: Pathways Mediating the Influence of PTSD on SMB: We will use the Self-regulation Model (SRM) to guide our exploration of the relationship between PTSD and asthma SMB via illness beliefs, emotional representations and symptoms perception (Figure 1 and 5).¹²⁴⁻¹²⁷ According to the SRM, people with chronic illness, like asthma, compare their somatic sensations (i.e., symptoms) to their “normal” self, and interpret deviations from “normal” in relation to their mental model of their illness, which in turn guides their SMB. Appraisal of the efficacy of their actions (i.e., improved asthma control) serves as a feedback loop to reinforce or modify SMB. The SRM posits five domains of cognitive representations of illness: identity (disease labels), cause (etiology and triggers), timeline (chronicity), consequences (perceived impact), and control (extent to which an illness can be controlled). For example, if asthma patients accurately perceive their respiratory symptoms (identity) and believe asthma is persistent (timeline) they will engage in SMB. The SRM also predicts that patients will be

 Mount Sinai	Protocol Title:	Assessing Inflammatory and Behavioral Pathways Linking PTSD to Increased Asthma Morbidity in WTC Workers
	Principal Investigator Name/Contact Info:	[name], DrPH [contact]; [contact]
	Primary Contact Name/Contact Info	[name], MS [contact]; [contact]
	Date Revised:	07/25/16
	Study Number:	IF# 1896970; GCO# 16-0945

adherent if they learn, via feedback loops, that their asthma medications can prevent symptoms (controllability). Emotional responses to asthma (i.e., worry, upset, or anxious) also influence SMB.¹²⁸⁻¹³⁴ The framework of the SRM is highly useful for identifying the modifiable beliefs and emotional mechanisms which underlie behaviors worth targeting for self-management support interventions.¹²⁷

We expect that PTSD may impact asthma SMB in several ways. WTC workers with PTSD may magnify asthma symptoms (identity) when they are actually experiencing negative emotions. Over-perception of symptoms could be a major barrier for internalizing positive feedback loops about medication effectiveness, leading to low adherence. WTC workers with PTSD and asthma may also misinterpret the causes of their asthma symptoms and thus, avoid situations that trigger the physical sensations they fear. Paradoxically, decreasing the frequency of PTSD symptoms via avoidance of perceived (not actual) asthma triggers may contribute to illness representations that focus more on this maladaptive avoidance, and less on SMB. Some patients view asthma as a chronic (timeline) inflammatory condition (cause), which requires adherence to daily ICS. Data from non-WTC asthma populations shows that patients with PTSD are more likely to view asthma as an acute, episodic disease.¹³⁵ This 'acute' representation of asthma has been associated to low medication adherence.¹²⁸ Patients with PTSD also tend to feel out of control (due to unexpected symptoms and catastrophic thoughts) and have lower self-efficacy, which has been linked to low ICS adherence.¹³⁶⁻¹³⁸

According to the SRM, emotional responses also influence SMB. As discussed above, patients with PTSD have emotional regulation difficulties; thus, strong negative emotional reactions to asthma may deplete WTC workers' self-regulatory resources managing emotions to the detriment of asthma SMB.¹³⁹ SRM has also shown that medication beliefs strongly predict ICS adherence.^{130,140} Negative affect in workers with PTSD may extend to patients' beliefs about ICS (e.g., side effects, dependence, etc.) negatively influencing adherence.^{133,141} Moreover, patients with PTSD may avoid asthma medications and awareness of symptoms because these factors may serve as trauma cues or reminders of 9/11, triggering memories of their WTC traumatic experiences. Thus, this coping style (avoidance) may lead to low medication adherence.^{22,142}

Absence of Interventions Integrating PTSD and Asthma Management: Despite the strong link between asthma and PTSD in WTC workers, there are no interventions aimed at managing both conditions. [name] is conducting a randomized clinical trial (RCT) to evaluate an integrative mind-body treatment, the 3RP, to improve the management of PTSD and lower respiratory symptoms in WTC workers (see preliminary data).¹⁴³⁻¹⁴⁵ The 3RP is an 8-session group-based program that seeks to promote the physiological, emotional, cognitive and behavioral effects of the relaxation response.¹⁴⁶ The 3RP program focuses on 3 major areas to decrease stress and build resiliency: 1) eliciting the relaxation response via sustained mental focus with an attitude of open receptive awareness; 2) promoting stress awareness and decreasing reactivity, which involves identification of the 5 components of one's stress response (thoughts, emotions, physical reactions, behaviors, and relationship changes) and learning skills (e.g., cognitive restructuring) to change these components; and 3) increasing use of adaptive

 
Mount Sinai
	Protocol Title:	Assessing Inflammatory and Behavioral Pathways Linking PTSD to Increased Asthma Morbidity in WTC Workers
	Principal Investigator Name/Contact Info:	[name], DrPH [contact]; [contact]
	Primary Contact Name/Contact Info	[name], MS [contact]; [contact]
	Date Revised:	07/25/16
	Study Number:	IF# 1896970; GCO# 16-0945

strategies by focusing on skills to promote positive growth and self-efficacy in response to stress. However, this intervention was not specifically developed for WTC workers with asthma and thus, does not address misperception of symptoms or disease SMB.

3) Setting of the Human Research

The study sites will include New York City (the Mount Sinai Hospital [MSH]) and Queens (Queens College – Northwell Health).

The research at Mount Sinai will take place in the Center for Advanced Medicine Building at [name]. The research at Queens College will take place at the Northwell Health Queens World Trade Center Health Program located at [name].

4) Resources Available to Conduct the Human Research

The study cohort will consist of a sample of 400 WTC workers with asthma enrolled in the MSH or Queens World Trade Center Health Programs. There will be 300 subjects enrolled at MSH and 100 at Queens. [name] will be responsible for overseeing data collection activities and quality of data collected. For the observational cohort study (Aims 1-3), we selected validated tools and electronic measures that are known to be highly valid and reliable. Data will be collected using electronic forms with built in logic patterns to minimize data entry errors. [name] will train research assistants in survey administration techniques and appropriate maneuvers for assessing lung function; Drs. [name] and [name] will train social workers or psychology graduate students in administration of the psychiatric interviews. We will randomly select 10% of audiotaped recordings of psychiatric interviews for [name] or [name] to rate for accuracy and to provide feedback to the graduate students. We will also conduct random checks of 10% of all collected data to assess for data entry errors, ranges of input values, missing data, and overall data quality. Similar methods will be used to monitor data collected as part of the pilot RCT (Aim 4). Study team members will meet monthly to review progress in recruitment goals, review preliminary results, and identify and resolve emerging problems.

Research staff will include:

Name	Title	Dept./Institution/Company
[name], MPH	PI	Medicine/ISMMS
[name]	Co-I	Preventive Health/ISMMS
[name]	Co-I	Clinical Immunology/ISMMS
[name]	Co-I	Psychiatry/ISMMS
[name]	Co-I	Psychiatry/ISMMS

 Mount Sinai	Protocol Title:	Assessing Inflammatory and Behavioral Pathways Linking PTSD to Increased Asthma Morbidity in WTC Workers
	Principal Investigator Name/Contact Info:	[name], DrPH [contact]; [contact]
	Primary Contact Name/Contact Info	[name], MS [contact]; [contact]
	Date Revised:	07/25/16
	Study Number:	IF# 1896970; GCO# 16-0945

Non-Key Personnel involved in study will be managed by the PI. Requisite certifications and records for these individuals will be included in the Regulatory Binder and Financial Conflicts of Interest will be reported on Sinai Central.

Qualifications of Key Personnel:

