Subjective Measures: Asthma Symptoms: Asthma control will be assessed with the Asthma Control Questionnaire (ACQ).^{197,198} It is available in English and Spanish and has excellent validity. Use of Beta2-agonists: Over-perception may be associated with increased use of quick relievers. Thus, we will use self-reports as well as Doser devices to objectively capture use of these medications for 4 weeks after each interview. Acute Resource Utilization: will include self-reported and electronic data on unscheduled office and ED visits and asthma-related hospitalizations. We will identify visits occurring at outside institutions by self-report and request external records. Although resource utilization can be considered a more objective measure it also is influenced by subjective perceptions concerning the need to seek help. Asthma quality of life: We will use the validated Mini Asthma Quality of Life Questionnaire (AQLQ); available in English and Spanish.¹⁹⁹

Independent Variables (Table): PTSD: Structured Clinical Interview (SCID): The SCID is considered the gold-standard psychiatric interview.²⁰⁰ The Bilingual version of the SCID will be used at the baseline, 6- and 12-month visits as the semi-structured psychiatric interview.²⁰⁰⁻²⁰² A psychology graduate student or social worker will administer the PTSD and the mood disorders modules. [name] and [name] will provide supervision for all diagnostic issues. Quality Assurance: We will randomly select 10% of audiotaped recordings for Drs. [name] or [name] to rate for accuracy and to provide feedback to interviewers. Patient Safety: If patients with active suicidal ideation are identified, the PIs will be notified to determine the need for an emergency psychiatric consult. Participants with PTSD will be given a list of counseling sites. Additionally, we will ask for patients' consent (signed HIPAA authorization) to alert their physicians about the SCID results after a lag of 4-6 weeks (to be able to assess the impact of PTSD on symptom perception and SMB). We will collect detailed data on medications for PTSD and/or depression by self-report and EMR review.

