Sputum Neutrophilia	0.25	0.30	106
Sputum Eosinophilia	0.50	0.25	107
IL-6, pg/ml	4 (2)	2	67

 Mount Sinai	Protocol Title:	Assessing Inflammatory and Behavioral Pathways Linking PTSD to Increased Asthma Morbidity in WTC Workers
	Principal Investigator Name/Contact Info:	[name], DrPH [contact]; [contact]
	Primary Contact Name/Contact Info	[name], MS [contact]; [contact]
	Date Revised:	07/25/16
	Study Number:	IF# 1896970; GCO# 16-0945

Power Calculations: Assumptions about the expected retention rate ($\geq 80\%$), the prevalence of PTSD ($\sim 30\%$) and the distribution of inflammatory markers were derived from our preliminary data and the literature.^{1,7,8} Under these assumptions, with 175 participants undergoing sputum induction, the study will be powered to test Aim 1 hypotheses (Table 3).

Aim 2. Examine the longitudinal association between PTSD and symptom perception in WTC workers with asthma: We will calculate the proportion of blows that each participant over-estimate using AM2 data. A probit transformation will be applied to normalize the proportion of over-perceived guesses; differences in the distribution of the transformed variable at each time point in participants with and without PTSD will be assessed with a t-test.²²⁷ We will use a GEE model to assess the association between PTSD and symptom perception over time.²²⁸ We will then fit a fixed effects model (i.e., limited to within subject variability) to assess the longitudinal effect of changes in PTSD symptoms (PCL scores) on symptom perception. We will repeat these analyses adjusting for potential confounders as described above.

[figure not shown]
We will also assess the correlation between subjective (ACQ scores, use of beta2-agonists, AQLQ scores) and objective (FEV₁) measures of morbidity separately in asthmatics with and without PTSD and apply a Fisher's z' transformation to assess if the association varies between these groups. Then, we will fit a GEE model with ACQ scores (or use of beta2-agonists/AQLQ) as the dependent variable and as predictors, FEV₁, PTSD status, and an interaction between PTSD and FEV₁. In this model, the interaction term will test whether the association between objective and subjective measures varies according to the participant's PTSD status.

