[name] will be responsible for overseeing data collection activities and quality of data collected. For the observational cohort study (Aims 1-3), we selected validated tools and electronic measures that are known to be highly valid and reliable. Data will be collected using electronic forms with built in logic patterns to minimize data entry errors. [name] will train research assistants in survey administration techniques and appropriate maneuvers for assessing lung function; Drs. [name] and [name] will train social workers or psychology graduate students in administration of the psychiatric interviews. We will randomly select 10% of audiotaped recordings of psychiatric interviews for [name] or [name] to rate for accuracy and to provide feedback to the graduate students. We will also conduct random checks of 10% of all collected data to assess for data entry errors, ranges of input values, missing data, and overall data quality. Similar methods will be used to monitor data collected as part of the pilot RCT (Aim 4). Study team members will

	Protocol Title:	Assessing Inflammatory and Behavioral Pathways Linking PTSD to Increased Asthma Morbidity in WTC Workers
	Principal Investigator Name/Contact Info:	[name], DrPH [contact]; [contact]
	Primary Contact Name/Contact Info	[name], MS [contact]; [contact]
	Date Revised:	07/25/16
	Study Number:	IF# 1896970; GCO# 16-0945

meet monthly to review progress in recruitment goals, review preliminary results, and identify and resolve emerging problems.

15) Community-Based Participatory Research

N/A

16) Sharing of Results with Subjects

Results will not be communicated with study participants as part of the study is not to influence decision making.

17) External IRB Review History

N/A

18) Control of Drugs, Biologics, or Devices

Note: The IDS has its own forms that must be completed and a review process that must be followed before the IDS representative will sign off on Appendix B for submission to the PPHS.

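### A consented physician alert 4-6 weeks after the SCID falls between the first 4-week window and the later ones, yet the Aim 2 and Aim 3 models pool these windows with no PTSD-by-period term

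*Combined protocol and SAP*

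**What the plan says.** Section 1 (Objectives) sets Aim 2 as follows: "Examine the longitudinal association between PTSD and symptom perception in WTC workers with asthma".

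The paragraph on the SCID (section f, Independent Variables) schedules the interview at baseline, 6 and 12 months. The team will seek "consent (signed HIPAA authorization) to alert their physicians about the SCID results", with a lag of 4-6 weeks, and the bracketed reason is "to be able to assess the impact of PTSD on symptom perception and SMB". The same paragraph states: "Participants with PTSD will be given a list of counseling sites". No timing is given for that list. Medications for PTSD and depression are recorded by self-report and chart review.

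Symptom perception is measured with the AM2 device in the 4 weeks after the baseline, 6-month and 12-month interviews (section f, Asthma Symptom Perception). Electronic adherence is monitored for 4 weeks after each interview (section f, Electronic Monitoring). The measures table also marks it at month 1, while section 10 (Payment) describes device returns only for the baseline, 6- and 12-month interviews.

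For analysis (section h, Aim 2): "We will use a GEE model to assess the association between PTSD and symptom perception over time". A t-test of the transformed over-perception proportion at each time point comes first, and a fixed-effects model of change in PCL score follows. Aim 3 uses a GEE with logit link, then a latent growth curve model (LGCM) at 0, 6 and 12 months. The confounder list, given under Aim 1 and referred to later, names neither disclosure nor PTSD treatment. Section 16 says: "Results will not be communicated with study participants as part of the study is not to influence decision making".

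**The concern.** The stated reason for the lag makes sense only if an alert could change perception or self-management. Having accepted that, the protocol protects one window and then analyses all of them together as though the alert had not happened. H2a and H3a ask how PTSD relates to perception and adherence in ordinary life. Some participants' later windows instead describe PTSD after the study has told a physician about it.

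A decision depends on the answer. Under Aim 4, perception training enters the pilot only if Aim 2 shows over-perception in participants with PTSD, and the beliefs to be addressed are those most strongly associated with self-management. A coefficient altered by the study's own notification could change what the pilot contains.

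**Working it through.** **Order of events**
- Weeks 0-4: first AM2 and adherence window, before any alert.
- Weeks 4-6: alert, for participants who authorise it.
- About weeks 4-8: an adherence window after the 1-month visit, if monitoring does follow every interview. It may straddle the alert.
- 4 weeks after the 6- and 12-month interviews: later windows, both following any baseline alert.

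With full retention, 2 of 3 AM2 windows (67%) follow the baseline alert. With 80% retention at both follow-ups it is 1.6/2.6 = 62%. At 30% PTSD prevalence, 0.30 × 400 = 120 participants have PTSD.

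**The plan's own figure.** The plan claims more than 90% power for a 10% increase in over-perception with 400 participants and a within-participant correlation of at least 0.8. It states neither the base rate nor the SD, so the figure can be bracketed but not confirmed. The check reads the effect as a 10-point difference, with a 30:70 split, two-sided alpha 0.05 (assumed for Aim 2) and three windows. The design effect is (1 + 2 × 0.8)/3 = 0.867, so the effective N is 400/0.867 = 461. Power is then 97.6% at SD 25 points and 90.7% at SD 30; more than 90% requires an SD of at most about 30.4. Treated as a binary outcome, a 10-point rise has 92.0% power from a base of 5% and 80.9% from 10%.

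**What the later windows add.** Information relative to one window is 3/(1 + 2 × 0.8) = 1.154, so the baseline-only standard error is √1.154 = 1.074 times the pooled one. At a correlation of 0.9 the ratio is 1.035. Starting from exactly 90% power, z = 1.960 + 1.282 = 3.242; 3.242/1.074 = 3.018; 3.018 − 1.960 = 1.058, giving about 85%.

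**What pooling could cost.** Let *c* be the share authorising the alert and *a* the proportional reduction of the PTSD difference in their later windows. The documents give neither. With equal window weights and a true difference of 10 points:

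pooled difference = 10 × [1 + 2(1 − *c a*)]/3

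| *a* (with *c* = 0.8) | Pooled difference | Bias | Power, SD 25 | Power, SD 30 |
|---|---|---|---|---|
| 0 | 10.0 | 0% | 97.6% | 90.7% |
| 10% | 9.47 | −5% | 96.1% | 87.4% |
| 25% | 8.67 | −13% | 92.7% | 81.2% |
| 50% | 7.33 | −27% | 82.3% | 67.2% |
| Baseline window only | 10.0 | 0% | 95.6% | 86.3% |

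At *c* = 1 and *a* = 50% the pooled difference is 6.67 (−33%). Pooling has lower power than the baseline window alone once *c a* exceeds 1.5 × (1 − 1/1.074) ≈ 0.10. That corresponds to *a* of about 13% at *c* = 0.8 and 21% at *c* = 0.5.

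**Sensitivity to the correlation structure.** The plan names an autoregressive structure for the Aim 1 GEE only. With a lag-one correlation of 0.8, the windows would weigh 0.45, 0.09 and 0.45 and the relative variance would be 0.818. The later windows would then carry about 0.55 of the weight instead of 0.67, and the baseline-only standard error would be 1/√0.818 = 1.106 times the pooled one.

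No comparable calculation was made for Aim 3; there the argument rests on the timing alone.

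**The case against.** The strongest case against is that nothing shows the alert will matter. It requires signed authorisation, and the authorisation rate, treatment uptake, effect size and direction are all unstated. A reader might infer that the study notifies a physician for every participant, that it certainly changes the effect, or that the bias runs towards no effect. The documents support none of these. Nor do they limit the alert to PTSD cases: it concerns SCID results, and the interview also covers mood disorders. These limits stand, and the table above is an illustration only.

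A reader might also extend the before/after split to the counselling list. With no stated timing, the list may precede even the first window, so the split is established for the alert only.

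The plan does contain partial protection. The Aim 2 t-test at each time point is an unpooled baseline contrast, but it is unadjusted, and Aim 3 describes no counterpart. Repeated SCID and PCL assessments may capture part of any change if PTSD status is time-updated, and a participant who has remitted is then not misclassified. The plan does not say whether status is updated.

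Finally, a reader might conclude that the baseline window should replace the pooled estimate as primary. Aim 2 is expressly longitudinal, so that would be a debatable trade and is not what this point asks for. Because all first windows precede the alert and all later AM2 windows follow it, a period term also cannot separate the alert from device practice, attrition or regression to the mean.

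**Conclusion.** The point holds in a limited form. The protocol's own justification treats the alert as able to disturb the association, its lag protects one window, and the main Aim 2 and Aim 3 models combine that window with later ones without any term for the difference. The pooled PTSD coefficient can therefore be altered by the study's own action, by an amount and in a direction that the documents do not determine. Under the assumed ranges at 80% authorisation, the Aim 2 estimate would be 5% to 27% too small for a 10% to 50% reduction, and unbiased if there is no reduction. The 7% standard-error figure rests on the plan's correlation of 0.8 with equal weights. The change is cheap and should be made before analysis, because alert dates are hard to recover later.

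Separately, section 16 on not communicating results and the SCID paragraph on giving a counselling list to participants with PTSD should be reconciled.

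**What to change.** - Add a PTSD × period term (pre-alert window versus later windows) to the H2a and H3a GEE models, and state how any adherence window after the 1-month visit is classed.
- Prespecify, as a key analysis, the adjusted pre-alert estimate (baseline SCID with the first 4-week window), reported alongside the pooled longitudinal estimate.
- State whether PTSD status in each model is fixed at baseline or time-updated.
- Record the authorisation date, the alert date and any new PTSD counselling, and use the PTSD medication data already collected in a sensitivity analysis.
- Report the LGCM, which needs all three time points, with the caveat that its later points follow any baseline alert.
- Reconcile section 16 with the SCID paragraph.

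The cost is analysis-plan wording and a few data fields. The pre-alert estimate has a standard error about 7% larger than the pooled one at a correlation of 0.8 (about 11% under the autoregressive structure above). A difference between periods must be read as a before/after contrast, not as proof of an alert effect. No change to the alert or to care is proposed.
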